3.1 General Design

The proposed project is a randomized, double-blind, placebo-controlled, parallel three-treatment arm phase II clinical evaluation of allopurinol, losartan, and placebo in hypertensive patients with severe OSA. The proposed trial is based on preliminary data suggesting that both of these available medications may reduce chemoreflex sensitivity and endothelial function in patients with OSA. Subject enrollment will be conducted on a rolling basis during the three year study period and subjects will be randomized (stratified by baseline CPAP adherence) to one of the three treatments. Randomization will be stratified based on three categories of baseline CPAP

Version: 23, 7-25-17

adherence: < 1 hr, 1 – 4 hrs, and > 4hrs of CPAP use on average per night. This will ensure balanced CPAP use between treatment arms. Allopurinol will be initiated at 300 mg daily and the dose will remain constant for the six-week study session. Losartan will be initiated at 50 mg daily and the dose will be increased to 100 mg after two weeks if systolic blood pressure is above 120 mm Hg and as long as serum creatinine and potassium do not significantly increase. Subjects with SBP between 120-100 mm Hg may increase to 100 mg if approved by physician. If the subject's serum creatinine (> 0.5 mg/dL) or serum potassium (above 5.0 mEq/L) significantly increase, or if the subject experiences a significant side effect from the medication (e.g. maculopapular rash) the subject will be discontinued from the study. If the subject does not tolerate the losartan dose increase to 100 mg, his/her dose will be reduced back to 50 mg by study staff at request of subject. If the subject tolerates the dose increase, the losartan dose will then remain unchanged from the second to sixth week of the study. Patients in the placebo group will receive placebo capsules daily for six weeks that are identical in appearance to the overencapsulated losartan and allopurinol.

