Subjects will have 24-hour ambulatory blood pressure and 24-hour Holter/Heart rate variability measurements taken* (Visit 2) on a day/night prior to Visit 3. Prior to starting study drug therapy, subjects will come to the Clinical Research Unit (CRU) at the University of Wisconsin for physiology/vascular study (Visit 3). Subjects recruited from the other recruitment sites will come to Madison for Visit 3. Subjects will arrive on day one of their study, and will have physiologic assessments taken before full overnight polysomnography and overnight Holter/Heart rate variability* is completed during night one (to determine severity of OSA). Prior to polysomnography, subjects will have muscle sympathetic nerve activity, forearm blood flow, cerebral blood flow velocity, plasma catecholamines, ventilation, blood pressure, and heart rate measured at rest under normoxic (room air) conditions and during graded levels of hypoxia (90%, 85% and 80% SaO₂). Following this, subjects will be allowed to return to normoxia (room air levels of oxygen ~ 21% oxygen) and after dinner will be hooked up for polysomnography and Holter/Heart rate variability*. The morning after polysomnography, subjects will have assessment of brachial artery flow-mediated vasodilation and nitroglycerin induced vasodilation measured by ultrasound. Then subjects will have aortic pulse wave velocity and augmentation index measured by arterial tonometry. The 2nd night subjects will stay overnight again in the VA Research Unit and have control of breathing studies completed (Pcrit and apnea threshold). Subjects will initiate study drug treatment and will return two weeks later for a blood pressure and heart rate (office blood pressure) measurement, CPAP assessment, and safety assessment to measure serum creatinine and serum potassium concentrations. This is standard safety monitoring in patients taking ARBs, and to maintain blinding, all subjects will have this monitoring completed. Subjects who do have clinically significant increases in serum creatinine (an increase > 0.5 mg/dL) or whose serum potassium increases to a concentration > 5.0 mEq/L will have their participation in the study terminated. Subjects continuing in the study will then complete four additional weeks of drug therapy. At the end of six weeks of study medication, subjects will have 24-hour ambulatory blood pressure and 24-hour Holter/Heart rate variability assessed one day and night.

Version: 23, 7-25-17

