4.4 Early Withdrawal of Subjects

4.4.1 When and How to Withdraw Subjects

Allopurinol

If a subject experiences an adverse effect that is thought to be significant or serious (e.g. renal impairment, maculopapular rash, etc.) subjects' participation in the study will be ended.

Losartan

If a subject experiences clinically significant/serious adverse effects (angioedema, myalgias, acute renal failure), their participation will be ended. If the subject experiences increases in serum creatinine (> 0.5 mg/dL) or serum potassium (above 5.0 mEq/L) the subject's participation in the study will be ended. Blood pressure will also be measured at the two week monitoring visit (Visit 4). The dose of losartan will increase to 100mg daily if systolic blood pressure is > 120 mm Hg. For a systolic blood pressure between 100-120 mm Hg the subject may have dose increased if approved by study physician. If the subject's blood pressure is $< 100/60$ mm Hg and if the patient is dizzy and symptomatic during the study, the subject will discontinue study medication and go off study. This can be done via a phone encounter or via an additional (unexpected) visit. It is possible the subject's participation will be terminated if the study physicians feel that is appropriate.

Subjects may also be withdrawn from the study if they are diagnosed with a new and significant medical problem (e.g. they are hospitalized for an acute illness or major medical condition). Subjects may also be withdrawn from the study if they consistently fail to adhere to the protocol requirements. Study physicians will communicate with subjects' regular physician about care plans upon their withdrawal from the study.

Version: 23, 7-25-17

Additional (Unexpected) Visit:

If a subject experiences an adverse event that requires them to be seen by study staff, they should be scheduled for a visit to their local center as soon as is feasible. The PIs should be notified immediately and the physician at the local site should see the subject during the visit. Depending on the complaint, the AE should be evaluated with appropriate objective measures (blood tests, blood pressure/heart rate measurements, etc.) and the case report forms for "Additional Visit" should be filled out (in subject binder). These forms include:

AE form
Vitals form
Additional visit form
AE log

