5.2 Treatment Regimen

Losartan 50 mg daily for two weeks, then increased to 100mg daily for 4 weeks

OR

Allopurinol 300 mg daily for 6 weeks

OR

Placebo capsule daily for 6 weeks

All three medications will be taken orally (in capsules) by subjects. The treatment regimen is summarized in Table 1.

Table 1. Treatment Regimen

Version: 23, 7-25-17

Arm	Treatment	Administered as:			
		Active Losartan 50mg Capsule Bottle A	Active Losartan 100mg Capsule Bottle B	Placebo	Allopurinol 300mg Capsule
Group I	Losartan	1 capsule daily on Days 1-14	1 Capsule daily on Days 15-42	None	None
Group II	Allopurinol	None	None	None	1 Capsule Daily on Days 1-42
Group III	Placebo	None	None	1 Capsule Daily on Days 1-42	None

Losartan subjects will take capsules from Bottle A for days 1-14, and capsules from Bottle B for days 15-42. If the subject's systolic blood pressure is > 120 mm Hg, the subject will continue to take capsules daily from Bottle A (days 15-42). If SBP is between 100-120 mm Hg, the subject may switch to bottle B with physician approval.

Allopurinol and Placebo will also have Bottle A and B for each treatment and will contain identical drug in Bottle A and Bottle B. Subjects will transition from Bottle A to Bottle B after day 14 in the allopurinol and placebo group. This is done to maintain study blinding.

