5.6.1 Pregnancy Testing and Birth Control

Women of child-bearing age are eligible subjects for this study. However, since study drugs are pregnancy rate "D" (losartan) and "C" allopurinol, female subjects will take a urine pregnancy test at Visit 1 to ensure they are not pregnant. A urine pregnancy test will be repeated at Visit 1A if the study visit occurs more than 90 days after Visit 1. Furthermore, a urine pregnancy test will also be given at Visit 3 prior to study drug dispensing. The Pregnancy and birth control case report form should be completed at Visit 1, Visit 1A (if applicable) and Visit 3. On this case report form the method of birth control used should be documented and subjects are instructed to keep their birth control consistent throughout the study. Methods of birth control that are acceptable while participating in this study include oral contraceptives, hormonal contraceptives, hormonal implants, contraceptive patches, NuvaRing, intrauterine device hormonal, intrauterine device non-hormonal, barrier method, spermicide, post-menopausal for greater than or equal to two (2) years, tubal ligation, bilateral oophorectomy, or hysterectomy, vasectomy, or abstinence. If a female is practicing abstinence, she should confirm this, including duration, and initial and date the case report form.

5.7 *Blinding of Study Drug*

Allopurinol and Losartan tablets will be over encapsulated and dispensed to subjects with a placebo using a double-dummy design. Both subjects and investigators will be blinded to study drug assignment. The PRC will have unblinding information should the need arise to unblind a subject's study drug assignment. To obtain unblinding information, please call the University of Wisconsin Pharmaceutical Research Center at [contact].

5.8 *Receiving, Storage, Dispensing and Return*

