5.8.2 Dispensing of Study Drug

The PRC performs all required study drug reconciliation and inventory procedures on a regular basis. PRC drug record logs record the movement of study drugs out of PRC storage and all medications are checked by a PRC pharmacist prior to dispensing to the subject and study staff. Amount of study drug on hand and dispensed is constantly tracked in PRC records. All study drugs will be dispensed by the PRC to subjects during Visit 3 in Madison. Subjects will receive all study drugs for the 6-week treatment period at Visit 3 and will receive instructions from investigators prior to starting therapy. Zolpidem (supplied by the PRC) will be given to subjects upon discharge from the CRU at VISITS 3 and 6 to be taken immediately before (9-10pm) the control of breathing study on night two.

6 Study Procedures

See Appendix 2

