- Day two: Ultrasound of blood vessels and heart; non-invasive tonometry; assessment of CPAP use; assessment of daytime sleepiness by completing the Epworth sleepiness scale; Study Medication dispensation (V3) and collection (V6); Control of Breathing Experiments during sleep stay at VA hospital. Subjects will receive zolpidem (sleeping medication) upon discharge from the CRU to be taken around 10pm at the start of the control of breathing study. (Ultrasounds performed in [name] laboratory; control of breathing studies performed by sleep technician). Subjects who do not have someone to drive them home, do not want to take a complimentary cab home or do not want to go back to the CRU to sleep and have breakfast prior to having a driver/cab take them home from Visits 3 and 6 may opt out of the control of breathing study on the second night. When a subject arrives for Visits 3 and 6, he/she will be asked if they have a driver to take them home, need a cab ride home or if they agree to go back to the CRU to sleep and have breakfast prior to having a driver/cab take them home after the control of breathing study.
- Visit 6 will also include AE Assessment and diary review in addition to the procedures mentioned above.

*Holter and Heart rate variability measurements are optional and will only be offered to UW subjects. They can choose to opt-in or opt-out of those procedures. Subjects who are non-CPAP users will have Holter monitoring done at Visits 3 and 6, but will not have Holter monitoring performed at Visits 2 and 5." The Holter monitors will be connected by UW Sleep Laboratory Technicians or study team personnel. Subjects may disconnect the Holter monitor on their own, or they may come back to UW-Madison to have the Holter monitor removed. A postage-paid envelope will be provided to subjects to return to Holter monitor by mail.

Visit 4: Monitoring visit (performed at each local site where subject was enrolled)

- measurement of blood pressure, heart rate, temperature, and height and weight, blood sample collection, Study drug compliance and diary review, AE assessment (all performed by local site coordinator or CRU nurses for Madison subjects)

Visit 7: One month Follow-up (performed at each local site where subject was enrolled)

- Subjects will be contacted by phone for completion of a final AE assessment (performed by local site coordinator)

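### After day 14 the written bottle rule depends on the arm: only losartan subjects may stay on or return to Bottle A, so 5.2 needs one rule for all arms

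*Combined protocol and SAP*

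**What the plan says.** **Losartan.** Section 3.1: "Losartan will be initiated at 50 mg daily and the dose will be increased to 100 mg after two weeks", provided SBP is above 120 mm Hg and creatinine and potassium are acceptable. Section 4.4.1, under its losartan heading: "For a systolic blood pressure between 100-120 mm Hg the subject may have dose increased if approved by study physician". Without approval the subject stays on 50 mg. If 100 mg is not tolerated, 3.1 adds: "his/her dose will be reduced back to 50 mg by study staff at request of subject". Section 5.2 expresses the dose as bottles (A is 50 mg, B is 100 mg), and its sentences about staying on Bottle A are in the paragraph that opens with losartan subjects.

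**Allopurinol and placebo.** Section 5.2: "Subjects will transition from Bottle A to Bottle B after day 14 in the allopurinol and placebo group". No blood pressure condition, approval step or return to Bottle A is attached. The two bottles hold the same drug in these arms, and 5.2 gives blinding as the reason for the switch.

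**Who knows what.** Section 5.7: "Both subjects and investigators will be blinded to study drug assignment"; the Pharmaceutical Research Center (PRC) holds the code. Section 5.8.2: "All study drugs will be dispensed by the PRC to subjects during Visit 3 in Madison". Section 6.2 describes the Visit 4 tasks as "all performed by local site coordinator or CRU nurses for Madison subjects". Section 3.1 says of the week-2 safety check: "to maintain blinding, all subjects will have this monitoring completed". That sentence covers the monitoring, not the choice of bottle.

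**The concern.** Visit 4 is where the bottle is chosen, and those present are not meant to know the arm. The rules as written ask them to act differently by arm. Because all drug is handed out at Visit 3, there is no dispensing step at Visit 4 in which the PRC could make the choice unseen.

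Each way of resolving this departs from something in the text:

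1. If the arm-specific wording is applied, Bottle A after day 14 marks losartan.
2. If the blood pressure and step-down rules are applied to everyone, some allopurinol and placebo subjects stay on or return to Bottle A, contrary to the unconditional sentence in 5.2.
3. If everyone is switched at day 14, losartan subjects at SBP 100-120 go to 100 mg without the approval that 3.1, 4.4.1 and 5.2 require.

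At stake are the blinding promised in 5.7, the same practice at every site, and the dose for some losartan subjects over the last four weeks.

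**Working it through.** The plan gives no figure to reproduce here, so the main check sets the written rules side by side.

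| Situation at or after day 14 | Losartan | Allopurinol, placebo (5.2) | Same? |
|---|---|---|---|
| 1. SBP > 120, laboratory values acceptable | B (3.1, 4.4.1) | B | Yes |
| 2. SBP 100-120, physician approves | B (3.1, 4.4.1, 5.2) | B | Yes |
| 3. SBP 100-120, not approved | A (3.1, 4.4.1, 5.2) | B | No |
| 4. SBP < 100, not withdrawn | A (implied: no increase is provided for) | B | No |
| 5. 100 mg not tolerated, reduction requested | Back to A (3.1) | No rule, so stays on B | No |

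The prescribed bottle differs by arm in 3 of 5 situations. It also differs in situation 1 if 5.2 is followed as printed, because 5.2 keeps losartan subjects with SBP above 120 on Bottle A, contrary to 3.1 and 4.4.1. The result above does not rely on that contradiction.

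**What the documents fix.**
- Period covered: days 15-42, that is 42 - 14 = 28 days; 28/42 = 67% of treatment. This is the length of the window, not a count of subjects.
- What Bottle A reveals: with three equal groups, as the per-group numbers in 7.1 imply, a subject is on losartan with probability 1/3 = 33%. Under the literal rule, Bottle A after day 14 means losartan.

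**What they do not fix.** Visit 4 blood pressures, the approval rate and the step-down rate are not given, so the number affected cannot be computed.

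**Residual clue under one common rule.** Let p be the probability of SBP at or below 120 at Visit 4, pL on losartan and pO in each other arm. With equal allocation and equal approval rates, and leaving out step-downs, P(losartan given Bottle A) = pL / (pL + 2 pO). All blood pressure inputs are assumptions (Normal distributions, same SD in every arm).

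| Losartan mean, SD | pL | Other arms equal | pO at +5 mm Hg | Result | pO at +10 mm Hg | Result |
|---|---|---|---|---|---|---|
| 135, 12 | 10.6% | 33.3% | 4.8% | 52.5% | 1.9% | 73.9% |
| 130, 12 | 20.2% | 33.3% | 10.6% | 48.9% | 4.8% | 67.9% |
| 130, 15 | 25.2% | 33.3% | 15.9% | 44.3% | 9.1% | 58.1% |
| 125, 15 | 36.9% | 33.3% | 25.2% | 42.2% | 15.9% | 53.8% |

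Example, last row at +5: 36.9 / (36.9 + 2 × 25.2) = 36.9 / 87.3, about 42%. A common rule therefore weakens the clue without removing it. These figures describe what remains after the fix, not harm from the present text.

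**The case against.** The strongest reply is that blinded staff can work with this text. Part of 5.2 is already in bottle terms and refers simply to the subject, so staff can seek physician approval for anyone at SBP 100-120 without the code. Allopurinol and placebo subjects have matching bottles for the sake of blinding, and the week-2 check is done in everyone for the same reason. The unconditional sentence for those arms can be read as a default, as the opening losartan sentence is, with the exceptions understood to apply to all. On that reading no allopurinol or placebo dose changes.

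Much of this stands. A common rule was probably intended, and it is too strong to infer that blinded staff cannot run Visit 4. It is also too strong to infer that the blind was broken: the available text gives no code holder a role at Visit 4, and 8.4 reserves unblinding for urgent medical need. Nor does it follow that losartan subjects will be moved to 100 mg without approval, since the approval condition appears in three sections.

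What does not stand is that intention settles the matter. Section 3.1 extends only the monitoring to all arms. Section 5.2 gives allopurinol and placebo an unqualified switch, and 3.1 and 4.4.1 state their rules for losartan alone. Sites would have to guess that the unqualified sentence has exceptions.

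Two limits apply. Section 6.1 is not in the available text, the appendices appear by title only, and the blinding scheme mentioned in 5.4 is not reproduced, so an operational instruction elsewhere cannot be excluded. Also, 5.7 names subjects and investigators; that study staff are blinded is inferred from 8.4, under which staff must contact others to unblind a subject.

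**Conclusion.** The point holds as a defect in the written rule. Read literally, the bottle after day 14 depends on the arm in 3 of 5 situations, and Bottle A in days 15-42 would mark losartan, which conflicts with 5.7. It rests on reading 5.2 as printed and on no overriding instruction in material not available.

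A reader might go further and infer bias in the primary outcome, the slope of muscle sympathetic nerve activity (MSNA). The documents do not support that. Section 6.2 has the principal investigators and a sleep technician performing the Day 1 procedures, which include nerve recording, and 9.4 opens Visit 4 data to all investigators. But 9.4 does not name bottle status among those data, the scoring procedure is not shown, and 7.2 has a blinded statistician do the analysis. Actual unblinding, the number affected and any effect on MSNA scoring remain undetermined. This is a minor to moderate correction.

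**What to change.** Replace the bottle wording in 5.2 with one rule for every subject in every arm, and cross-refer to it from 3.1 and 4.4.1:

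- After the Visit 4 laboratory and blood pressure check, go to Bottle B if SBP is above 120 mm Hg, or if it is 100-120 and a study physician approves.
- Otherwise stay on Bottle A.
- A subject who does not tolerate Bottle B may return to Bottle A unless a withdrawal criterion in 4.4.1 applies.

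This also replaces the 5.2 sentence that keeps subjects with SBP above 120 on Bottle A. Bottle status should stay visible to investigators, because 9.4 wants them to see Visit 4 data for safety and medication monitoring. At most, ask that those who score MSNA do not see it.

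**Cost.** A few sentences, and no change of dose on allopurinol or placebo. Confirm that Bottle A supply covers days 1-42 in every arm: Table 1 assigns it days 1-14 for losartan, so a subject who stays on it needs 28 more capsules, and all drug is handed out at Visit 3. The downside is that Bottle A remains a partial clue if losartan lowers SBP more than the other treatments. Under the assumptions above, the chance that a Bottle A subject is on losartan is 42-53% for a 5 mm Hg difference and 54-74% for 10 mm Hg, against 33% with no difference.

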On a following night, subjects will return to Madison for physiology studies, overnight polysomnography and Holter/heart rate variability measurements*, vascular function measures and control of breathing studies the 2nd night to assess the study drug effects on variables measured at baseline. Subjects will be instructed not to consume caffeine (both solid and liquid forms) after midnight the night before they are admitted to the CRU and after 8pm on night 1. Subjects may consume caffeine after the physiology study on Day 1 and before 8pm on Day 1. Subjects will also be instructed not to smoke after 10 pm once they are admitted to the CRU until discharged. Subjects will not be allowed to participate in the study if they are unable to refrain from smoking after 10 pm for up to 24 to 48 hours once they are admitted to the CRU until discharged.

*Holter and Heart rate variability measurements are optional and will only be offered to UW subjects. They can choose to opt-in or opt-out of those procedures. Subjects who are non-CPAP users will have Holter monitoring done at Visits 3 and 6, but will not have Holter monitoring performed at Visits 2 and 5. The Holter monitors will be connected by UW Sleep Laboratory Technicians or study team personnel. Subjects may disconnect the Holter monitor on their own, or they may come back to UW-Madison to have the Holter monitor removed. A postage-paid envelope will be provided to subjects to return to Holter monitor by mail.

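### Table 1 schedules the last capsule on Day 42, but the two-day Visit 6 falls at or after that day, so its drug-effect tests, possibly including the primary MSNA recording, have no dose scheduled that day.

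*Combined protocol and SAP*

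**What the plan says.** **Dosing.** Table 1 in section 5.2 gives the losartan arm its 100 mg bottle as "1 Capsule daily on Days 15-42"; allopurinol and placebo also run to Day 42. A losartan subject kept on the lower strength also ends there: "the subject will continue to take capsules daily from Bottle A (days 15-42". Section 5.8.2 makes a single hand-out for the six weeks: "All study drugs will be dispensed by the PRC to subjects during Visit 3 in Madison".

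**Final measurements.** Section 3.1 says: "At the end of six weeks of study medication, subjects will have 24-hour ambulatory blood pressure". Then: "On a following night, subjects will return to Madison for physiology studies". Sections 4.3 and 5.5 place Visit 6 six weeks after the first dose.

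**Order within the visit.** MSNA is recorded on day one, before the overnight sleep study. For the vascular tests, section 3.1 says: "The morning after polysomnography, subjects will have assessment of brachial artery flow-mediated vasodilation". The breathing study is on the second night, and section 5.8.2 times the zolpidem for it: "to be taken immediately before (9-10pm) the control of breathing study on night two". Section 3.1 gives the purpose of the Visit 6 tests, including "vascular function measures and control of breathing studies the 2nd night to assess the study drug effects on variables measured at baseline". Flow-mediated vasodilation, pulse wave velocity, augmentation index and apnea threshold are secondary outcomes in section 3.3. The MSNA slope is the primary outcome in section 3.2.

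The text supplied gives no clock time for the capsule, no visit window, no maximum gap between Visits 5 and 6, and no instruction on dosing during Visit 6. Appendices 1 and 2 are listed but were not available.

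**The concern.** The visit meant to measure drug effect runs past the last scheduled dose. A subject who follows Table 1 exactly takes nothing on day two of Visit 6 and, if the visit starts on Day 43, nothing on day one either. A subject with leftover capsules, or one told informally to carry on, may keep dosing. The treatment state at the final measurement could then differ between subjects, and the plan has no field that would show it.

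The two active drugs leave the blood at very different speeds. Section 1.3 justifies the losartan dose by metabolite levels high enough to block angiotensin II, so the level at testing matters on the protocol's own reasoning. If an effect fades with the level, the comparison with placebo is diluted, most plausibly for losartan.

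**Working it through.** **Inputs.** Last scheduled capsule: Day 42 (Table 1). Half-lives: E-3174, the active losartan metabolite, 4-9 h; oxypurinol 17-21 h (section 1.3). Breathing study: 9-10 pm on night two (section 5.8.2). Assumed, because not stated: capsule at 9 am or 9 pm; MSNA between 11 am and 7 pm; vascular tests at 9 am.

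**Reproducing the plan's figures.** Five half-lives give 5 x 4 = 20 h to 5 x 9 = 45 h for E-3174, and 5 x 21 = 105 h (4.4 days) for oxypurinol. Both match section 1.3. Treatment length is 14 + 28 = 42 days, as in Table 1.

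**Day count.** Six weeks after Day 1 is Day 1 + 42 = Day 43. A 24-hour recording at the end of week six, followed by Visit 6 on a later night, also points to Day 43 or after. Day 42 is the earliest tenable start. Day two of the visit is therefore Day 43 or Day 44, or later. Covering it takes 1 or 2 more daily capsules.

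**Decay.** Share of the starting level left after t hours = 2^(-t / half-life).

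- 24 h: E-3174 1.6%-15.7%; oxypurinol 38%-45% (an ordinary once-daily trough)
- 26 h: E-3174 1.1%-13.5%; oxypurinol 35%-42%
- 34 h: E-3174 0.3%-7.3%; oxypurinol 25%-33%
- 36 h: E-3174 0.2%-6.3%; oxypurinol 23%-30.5%
- 48 h: E-3174 0.02%-2.5%; oxypurinol 14%-21%
- 60 h: E-3174 0.003%-1.0%; oxypurinol 9%-14%

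**Hours since the last scheduled capsule:**

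| Capsule | Visit 6 starts | MSNA | Vascular | Breathing |
|---|---|---|---|---|
| 9 am | Day 43 | 26-34 | 48 | 60 |
| 9 am | Day 42 | dosing day | 24 | 36 |
| 9 pm | Day 43 | 14-22 | 36 | 48 |
| 9 pm | Day 42 | 14-22 | 12 | 24 |

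In the first row MSNA is recorded with 0.3%-13.5% of E-3174 and 25%-42% of oxypurinol left. The night-one sleep study, if it starts at about 9 pm, is then at 36 h. In the last row every test is within 24 h of a capsule. Because no upper window is stated, 60 h is not a ceiling.

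**Supply.** If Bottle A covers Days 1-42 and Bottle B Days 15-42, subjects hold 42 + 28 = 70 capsules for 42 doses, so 28 are spare. For a losartan subject moved to Bottle B, the spares are the 50 mg strength. If the bottles hold 14 and 28, none are spare. Fill counts are not stated.

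**The case against.** The best reply is that testing on drug was clearly intended and that Days 1-42 is only a label for six weeks. There is support for this. Section 6.2 lists drug collection under day two of Visit 6. Subjects bring their medication to that visit. Uric acid and plasma renin activity at six weeks serve as adherence markers. The 30-day safety follow-up is counted from the last dose in section 8.1 and from Visit 6 in section 8.2, as if the two coincided. Appendix 1 or 2 may contain the instruction. All of this stands as evidence of intent. It does not change Table 1, which is the only dosing schedule in the text supplied and stops too early for that intent.

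Two more objections stand. Some subjects never reach the longest gap, because they may opt out of the night-two study or be barred from it by other medication. And E-3174 falls faster than oxypurinol at any daily trough: 1.6%-15.7% against 38%-45% at 24 h. A reader might infer that the Day 42 stop creates the unlike conditions for the two drugs. It only widens a difference that exists under perfect dosing.

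A reader might also infer that the primary outcome is measured off drug and is compromised. The documents do not support that: nobody is told to stop before Visit 6, the capsule time is not stated, and an evening capsule keeps MSNA within 24 h even with a Day 43 start. The opposite inference, that MSNA is safe because it comes on day one, is not supported either. It needs a Day 42 start or a late capsule, and no section fixes one.

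**Conclusion.** The point holds as a gap between the dosing schedule and the visit schedule. Read literally, the vascular and night-two breathing tests have no capsule scheduled on their day under either start day. The primary MSNA recording has none if Visit 6 starts on Day 43, which is the more natural reading.

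The consequence ranges from none (evening capsule, Day 42 start) to tests 26-60 h after the last scheduled dose (morning capsule, Day 43 start), and longer if the visit slips. These figures rest on first-order decay, the half-lives in section 1.3 and assumed clock times.

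Plasma level is not effect. The documents give no offset time, and some of the proposed mechanisms may outlast the drug, so neither bias nor lost power can be sized. This is an inexpensive improvement that should be made. It is not evidence that the primary comparison fails. Confidence is medium, because the two appendices were not seen.

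**What to change.** - In Table 1, section 5.2 and section 3.1, state that study drug continues once daily in all arms, from the bottle in use, through the last Visit 6 measurement (MSNA, sleep, vascular and breathing tests), and is collected after that.
- State a Visit 6 window and a maximum Visit 5-to-Visit 6 interval. Dispense enough of each bottle at Visit 3 to cover the 1-2 extra days plus that window.
- At the Visit 6 diary review that already exists, record the clock time of the last capsule before MSNA and before the day-two tests.
- If Appendix 1 or 2 already says this, align sections 5.2 and 3.1 with it.

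The cost is 1-2 more capsules (possibly already held as spares) and 1-2 more days of exposure per subject on the stated timing, one data field and a few sentences. The change keeps each test within about one ordinary dosing interval. It does not equalize dose-to-test time, but the recorded times would show what variation remains.
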